# 1.9. Study Rationale

The purpose of this study is to assess the efficacy of statin therapy for patients with sepsisinduced ALI. By restricting the population to those we believe to have both infection and evidence for systemic inflammation (sepsis), this study targets a disease process and population that has been best studied in animal models, observational trials and two small RCTs. By focusing on sepsis-induced ALI we have selected a group that has a higher disease burden than sepsis alone and thus likely to have both increased mortality and an increased opportunity for benefit, including a reduction in the requirement for mechanical ventilation. We completed a survey of patients with suspected or known infection, SIRS, and acute hypoxic respiratory failure admitted to ARDS Network ICUs and found that 18% of patients were receiving statins prior to admission. Less than one percent of patients received statins during their ICU stay. We also identified that 88% of patients with sepsis-induced respiratory failure had bilateral infiltrates and thus met the definition for ALI. Given that the mortality and ventilator days are significant in patients with sepsis-induced ALI, we believe there is real opportunity for improved clinical outcomes if the right interventional agent can be identified. In choosing mortality and VFDs as the primary and secondary outcomes, we will be able to detect changes in clinical outcomes that are important to patients and to society.

# 2. Objectives

### 2.1. Primary Objectives

To assess the efficacy and safety of rosuvastatin in patients with sepsis-induced ALI

# 2.2. Hypothesis

Rosuvastatin therapy will improve mortality in patients with sepsis-induced ALI.

# 3. End-Points

Analysis of the primary, secondary and other endpoints will be conducted on an intention-totreat (as randomized) basis.

# 3.1. Primary Endpoint

The Primary efficacy measure is hospital mortality to day 60.

# 3.2. Secondary End Points

Ventilator Free Days or VFDs to day 28 are defined as the number of days from the time of initiating unassisted breathing to day 28 after randomization, assuming survival for at least two consecutive calendar days after initiating unassisted breathing and continued unassisted breathing to day 28. If a patient returns to assisted breathing and subsequently achieves unassisted breathing to day 28, VFDs will be counted from the end of the last period of assisted breathing to day 28. A period of assisted breathing lasting less than 24 hours and for the purpose of a surgical procedure will not count against the VFD calculation. If a patient was receiving assisted breathing at day 27 or dies prior to day 28, VFDs will be zero. Patients transferred to another hospital or other health care facility will be followed to day 28 to assess this endpoint.

#### 3.3. Other Secondary Endpoints

- 1. Hospital mortality to day 28
- 2. Organ failure free days at day 14
- 3. ICU-free days at day 28
- 4. Hospital-free days at day 60
- 5. Increase in PaO2/FiO2 ratio and Oxygenation Index on study days 1-7

- 6. VTE at day 14
  - a) Documented by venous ultrasound, impedance plethysmography, contrast venography, ventilation-perfusion lung scan, CTPA/V, or pulmonary angiography
- Composite end-point of myocardial infarction, bowel ischemia or ischemic stroke to day 28
- 8. Arrhythmias during ICU stay or day 14, whichever is first
- 9. Development of acute kidney injury
- 10. Changes in plasma concentrations of CRP from day 0 to day 6 and 14. Blood and urine will be reserved beyond study completion for additional biomarker studies.

The rationale for the primary and first secondary endpoint is given in section 1.9. VTE is an endpoint because statins have been reported to be associated with lower rates of VTE in ambulatory patients. Cardiovascular endpoints are being assessed given the high prevalence of occult cardiovascular disease and the known benefits of statins in this population. The development of AKI is an endpoint as observational studies suggest statins prevent AKI. CRP is a surrogate marker of systemic inflammation and is expected to be reduced by statins.

# 3.4. Definition of Organ Failure:

Organ failure days are defined according to the most abnormal vital sign or lab value for each calendar day, according to the Brussels Organ Failure Table using the clinically significant organ failure thresholds. Patients will be followed for development of organ failures to death, hospital discharge or study day 14, whichever comes first. Each day a patient is alive and free of an organ failure will be scored as an organ failure-free day. Any day that a patient is alive and free of all 5 organ failures will represent days alive and free of all organ failure.

# 3.5. Focused Safety Analysis:

The incidence of elevations in CK > 10 times ULN, AST > 8 times ULN, and ALT > 8 times ULN measured on days 0, 1, 3, 6, 14, and 21 (additional CK on day 10).

# 4. Study Population and Enrollment

# 4.1. Number/Source/Screening

The trial will accrue a maximum of 1000 patients over a 2-3 year interval. Patients with sepsisinduced ALI will be recruited from intensive care units at NIH ARDS Network hospitals. Study coordinators will screen intensive care units daily to identify potential candidates for enrollment. Permission to approach patients and/or their families will be requested from the attending physicians. All patients meeting the inclusion criteria will be entered into a screening log. If the patient is not enrolled, the screening log will include information explaining why enrollment did not occur (exclusion criteria, attending physician denial, patient refusal, etc. see Appendix J for a listing of the deidentified data to be collected on screened, non-enrolled subjects).

#### 4.2. Inclusion Criteria

- 1. Systemic inflammatory response syndrome (SIRS) defined as meeting at least 1 of the following 3 criteria for a systemic inflammatory response. One of the SIRS criteria must be either the WBC criteria (a) or the body temperature criteria (b) :
  - a. White blood cell count >12,000 or <4,000 or >10% band forms
  - b. Body temperature >38°C (any route) or <36°C (accepting core temperatures only; indwelling catheter, esophageal, rectal)
  - c. Heart rate (> 90 beats/min) or receiving medications that slow heart rate or paced rhythm
- 2. Suspected or proven infection: Sites of infection include thorax, urinary tract, abdomen, skin, sinuses, central venous catheters, and bacterial meningitis (Appendix A).
- 3. ALI as defined by acute onset of:
  - a.  $PaO_2 / FiO_2 \le 300$  (intubated). If altitude > 1000m, then  $PaO_2 / FiO_2 \le 300$  x (PB/760), and
  - b. Bilateral infiltrates consistent with pulmonary edema on frontal chest radiograph, and
  - c. Requirement for positive pressure ventilation via an endotracheal tube, and
  - d. No clinical evidence of left atrial hypertension, or if measured, a Pulmonary Arterial Wedge Pressure (PAOP) less than or equal to 18 mm Hg. If a patient has a PAOP > 18 mmHg, then the other criteria must persist for more than 12 hours after the PAOP has declined to  $\leq$  18 mmHg, and still be within the 48-hour enrollment window.

"Acute onset" is defined as follows: the duration of the hypoxemia criterion (#1) and the chest radiograph criterion (#2) must be  $\leq 28$  days at the time of randomization. Opacities considered "consistent with pulmonary edema" include any patchy or diffuse opacities not fully explained by mass, atelectasis, or effusion or opacities known to be chronic (> 28 days). The findings of vascular redistribution, indistinct vessels, and indistinct cardiac borders are not considered "consistent with pulmonary edema".

All ALI criteria (3a-d above) must occur within the same 24 hour period. The onset of ALI is when the last ALI criterion is met. Patients must be enrolled within 48 hours of ALI onset and no more than 7 days from the initiation of mechanical ventilation. SIRS criteria must occur within the 72 hours before ALI onset **and the 24 hours after ALI onset**. Information for determining when these time window criteria were met may come from either the Network hospital or a referring hospital reports.

#### 4.3. Exclusion Criteria:

- 1. No consent/inability to obtain consent
- 2. Age less than 18 years
- 3. More than 7 days since initiation of mechanical ventilation (Example: If day of randomization is day "zero", date of current intubation cannot be prior to day "negative 7")
- 4. More than 48 hours since meeting ALI inclusion criteria

- 5. Patient, surrogate, or physician not committed to full support (Exception: a patient will not be excluded if he/she would receive all supportive care except for attempts at resuscitation from cardiac arrest).
- 6. Unable to receive or unlikely to absorb enteral study drug (e.g. patients with partial or complete mechanical bowel obstruction, intestinal ischemia, infarction, and short bowel syndrome)
- 7. Rosuvastatin specific exclusions
  - a. Receiving a statin medication within 48 hours of randomization
  - b. Allergy or intolerance to statins
  - c. Physician insistence for the use or avoidance of statins during the ICU stay
  - d. CK, ALT or AST > 5 times the upper limit of normal (ULN) except in patients with elevated CK who have an identifiable cause of CK elevation other than statin therapy providing the CK levels have fallen at least 10 % in the two most recent measurements and are less than 10 times ULN at randomization and the patient had not received any statins in the 30 days prior to enrollment (Example: A patient with staphylococcal sepsis has a CK of 3000 (10 times ULN). The next measurement is 2400 (8 times ULN). This patient would not be excluded for the elevated CK provided that no statins had been administered in the previous 30 days because the CK is now less than 10 times ULN, and the value has fallen more than 10% in the last two measurements).
    - i. If not available, a blood sample will be obtained after informed consent and results must be below protocol specified thresholds prior to randomization..
    - ii. CK, ALT and AST values obtained up to 24 hours prior to randomization are acceptable baseline values (e.g. Day zero) for both randomization and administration of the first dose of study.
  - e. Diagnosis of hypothyroidism and not on thyroid replacement therapy
  - f. Pregnancy or breast feeding
  - g. Receiving niacin, fenofibrate or cyclosporine, gemfibrozil, lopinavir, ritonavir, atazanavir, daptomycin while on study drug
- 8. Severe chronic liver disease (Child-Pugh Score 12-15)

Measure	1 point	2 points	3 points	Units
Bilirubin (total)	<34 (<2)	34-50 (2-3)	>50 (>3)	µmol/l (mg/dl)
Serum Albumen	>35	28-35	<28	g/l
INR	<1.7	1.71-2.20	> 2.20	no unit
Ascites	None	Suppressed with medication	Refractory	no unit
Hepatic Encephalopathy	None	Grade I-II (or suppressed with medication)	Grade III- IV (or refractory)	no unit

- 9. Moribund patient not expected to survive 24 hours
- 10. Chronic respiratory failure defined as  $PaCO_2 > 60$  mm Hg in the outpatient setting
- 11. Home mechanical ventilation (noninvasive ventilation or via tracheotomy) except for CPAP/BIPAP used solely for sleep-disordered breathing
- 12. Diffuse alveolar hemorrhage from vasculitis
- 13. Burns > 40% total body surface
- 14. Interstitial lung disease of severity sufficient to require continuous home oxygen therapy
- 15. Unwillingness or inability to utilize the ARDS network 6 ml/kg PBW ventilation protocol
- 16. Cardiac disease classified as NYHA class IV
- 17. Myocardial infarction in the previous 6 months
- 18. Intraparenchymal Central Nervous System (CNS) bleed within a month of randomization.

#### **Rationale for Exclusions**

Patients less than 18 years old are excluded because of limited clinical trial data with rosuvastatin in subjects younger than 18 years. Criteria 5, 8, 9, 10, 11, 14, 16, exclude patients unlikely to survive to the primary study endpoint or whose underlying condition or ventilator management complicates assessment of the secondary endpoint of VFDs. Criterion 7 excludes patients who are more likely to experience an adverse reaction or in whom it is more difficult to detect an adverse reaction to statins should one occur. Patients with diffuse alveolar hemorrhage (criterion 12) are excluded because the mechanism of lung injury is different from ALI due to infection. Patients with large burns (criterion 13) are also excluded as conservative fluid management may be contraindicated. Patients with advanced heart failure (criterion 16) are excluded because distinguishing ALI from pulmonary edema may be difficult and patients with both ALI and advanced CHF are unlikely to survive to the primary study endpoint.

#### 4.4. Enrollment, Randomization, and Study Initiation Time Window

All ALI criteria (4.2.3a-d above) must occur within the same 24 hour period. The onset of ALI is when the last criterion is met. Patients must be enrolled within 48 hours of ALI onset and no more than 72 hours from the initiation of mechanical ventilation. SIRS criteria must occur within the 48 hours before and 24 hours after ALI onset. Information for determining when these time window criteria were met may come from either the Network hospital or a referring hospital reports. Following randomization, the low tidal volume protocol for mechanical ventilation and the fluid management strategy must be initiated within one and four hours respectively (if not already being utilized).

#### 4.5. Informed Consent

Informed consent will be obtained from each patient or surrogate before enrollment in the trial. No study procedures will be conducted before obtaining informed consent.

#### 4.6. Randomization

After informed consent is given, an assignment will be made by computer-generated randomization to administer either statin therapy or placebo. The randomization system will be based on Interactive Voice Response System (I.V.R.S.) technology or a web-based system. Each research coordinator will have a unique Personal Identification Number (PIN) which must be entered when using the system. A treatment assignment and individual subject identification number will be assigned. An emailed confirmation will follow to the study site. The randomization will be stratified by institution, and by shock at study entry to one of the two study arms.

### 4.7. Minorities and Women

Gender and racial patient subsets were considered by the NHLBI in selecting the Network Centers. The demographic profiles of the Centers selected for the Network show that the aggregate patient population contains representative proportions of minorities and women. Recruitment of minorities and women will be monitored by the Network Coordinating Center. If necessary, additional recruitment efforts will be made at specific centers to ensure that the aggregate patient sample contains appropriate gender and minority subsets. Pregnant women will be excluded because of the lack of safety data for statin use during pregnancy.

# 5. Study Procedures

If a pregnancy test, ALT, AST or CK are not available before informed consent, blood or urine tests will be obtained after informed consent but before randomization to ensure eligibility. Patients excluded on the basis of tests obtained in this manner will not be included in the intent-to-treat population.

# 5.1. Statin or Placebo Administration

Rosuvastatin or placebo will be administered through an enteral feeding tube or administered orally following extubation when patients are able to safely take oral medications. The type and placement of the enteral feeding tube (nasogastric, nasoenteric, PEG, orogastric, oroenteric, etc.) and the ability to safely take oral medications will be determined by the patient's primary team. Study drug will be blinded with an identical appearing placebo.

The first study drug dose (rosuvastatin or placebo) will be administered within 4 hours of randomization as a loading dose of 40 mg.

- 1. Subsequent doses will be at 10 am daily (+/- 4 hours) starting on the next calendar day as a maintenance dose of 20 mg.
- 2. If for any reason a maintenance dose is not administered at the intended time, it may be administered subsequently but not more than 12 hours after the intended time of administration.

Should the time be > 12 hours since last scheduled dose, the patient will not receive a dose on that study day but will be given a loading dose on the next calendar day. Maintenance dosing will continue on subsequent days.

Daily doses will be reduced by 50% for patients with a creatinine level greater than or equal to 2.8 mg/dL who are not on renal replacement therapy. Loading doses will not be reduced.

Daily dosing:

- Each subject will receive full dose if last known creatinine value less than 2.8 mg/dL.
- Each subject will receive half dose if last known creatinine value greater than or equal to 2.8 mg/dL (unless receiving renal replacement therapy in which case a full dose will be given).

If used, antacids should be administered no closer than 6 hours before or after administering rosuvastatin to avoid affecting absorption of study drug. The dosage need not be adjusted for ketoconazole, erythromycin, itraconazole, fluconazole, warfarin or digoxin.

# 5.2. Drug Level Specimens (venous blood)

The 40 mg loading dose and 20 mg maintenance dose are mid-range doses and were selected to quickly achieve and maintain plasma levels of rosuvastatin the range of 10-70 ng/ml. Plasma peak and trough levels of rosuvastatin will be obtained to determine the relationship, if any, of plasma levels to either the pleiotropic effects or the toxicities of statins. Trough levels will be drawn prior to the day 6 (+/- 2 day) dose. Peak levels will be drawn 3-5 hours after the dose.

# 5.3. Completion of Study Drug Administration

Patients will be considered to have completed the study drug administration portion of the study and the study drug will be stopped when one of the following conditions is met, whichever comes first:

- 1. 28 days after randomization or 3 days after ICU discharge (whichever comes first)
- 2. Discharge from study hospital
- 3. Death

Note: If patient is readmitted to the ICU while still on study drug before day 28, study drug should continue until three days after the next ICU discharge or day 28, whichever comes first. If the study drug administration has been completed and the patient is subsequently readmitted to the ICU, no further study drug should be administered.

The optimal duration of statin therapy for sepsis-induced ALI is unknown. The decision to examine a relatively long duration of therapy of up to 28 days was based on observational trials showing benefit with little or no toxicity when statins were continued throughout the ICU and hospital course. Furthermore, statin use in observational studies was of long duration prior to admission. The relative ease of once daily oral study drug administration was also considered in determining the duration of therapy.

#### 5.4. Premature Withdrawal from Treatment

The study drug will be discontinued if a patient develops an increase in either CK > 10 times ULN, AST > 8 times ULN, or ALT > 8 times the ULN, or if patient develops an intraparenchymal CNS bleed. Study drug will also be discontinued if niacin, fenofibrate, cyclosporine, gemfibrozil, lopinavir, ritonavir, atazanavir, daptomycin are administered, or if primary care team or surrogate decision maker request. Data collection will continue on these patients, including the type and dose of any statin used as part of usual care following withdrawal of study drug.

#### 5.5. Ventilator Procedures

Ventilator management, including weaning, will follow the modified ARDS Network lower tidal volume (6 ml/kg PBW) protocol (Appendix D). If not already being utilized, this low tidal volume protocol for mechanical ventilation must be initiated within one hour of randomization. Since the time a patient achieves unassisted ventilation affects the secondary endpoint, VFDs, and because recent evidence-based consensus recommendations have identified a best practice for weaning, weaning strategy will also be controlled by protocol rules in accordance with these evidence-based recommendations. This will assure similar weaning methods and provide potential benefit to both study groups. This newer weaning strategy is a simplified version of the protocolized weaning strategy used in prior ARDS Network studies (see Appendix D).

### 5.6. On-Study Fluid Management

Fluid management during shock will not be prescribed. In subjects who are not in shock, a conservative fluid management approach will be required. This conservative fluid management approach will represent a simplification of the algorithm utilized in the ARDS Network FACTT study (see Appendix E). If not already being utilized, this conservative fluid management approach must be initiated within four hours of randomization and continued until the subject has reached unassisted breathing (UAB) or study day 7, whichever occurs first.

# 6. Data Collection

#### 6.1. Background Assessments

- 1. Demographic and Admission Data
- 2. Pertinent Medical History and Physical Examination
- 3. Height; gender, measured body weight (MBW); calculated predicted body weight (PBW).
- 4. Time on ventilator prior to enrollment
- 5. Type of Admission
  - a. Medical
  - b. Surgical scheduled
  - c. Surgical unscheduled
  - d. Trauma

- 6. Alcohol Use Disorders Identification Test (AUDIT) tool (Appendix I)
- 7. Acute or Chronic renal failure and use of dialysis
- 8. Survey of smoking history including:
  - Ever smoker (> 100 cigarettes in lifetime)?
  - If yes, current smoker?
  - Estimate of pack years (# packs per day) x (# years smoked)
  - If former smoker, when did the subject quit smoking?

# **6.2.** Baseline Assessments

The following information will be recorded during the 24 hour interval preceding randomization. If more than one value is available for this 24 hour period, the value closest to the time of randomization will be recorded. If no values are available from the 24 hours prior to randomization, then values will be measured post randomization but prior to initiation of study drug.

- 1. APACHE III Score
- 2. CAM-ICU delirium screening assessment and RASS or RIKER sedation score at select hospitals
- 3. Vital Signs: Heart rate, systolic and diastolic blood pressure, body temperature, MAP, CVP.
- 4. Ventilator mode (including non-invasive ventilation), tidal volume FiO2 and PEEP, inspiratory plateau pressure, and mean airway pressures. If on a pressure-cycling mode, peak pressure during inspiration will be assumed to be the plateau pressure.
- 5. Arterial PaO2, PaCO2, pH and SpO2
- 6. Serum CK, AST and ALT
- 7. Date and time of all creatinine determinations in the 48 hours prior to enrollment.
- 8. Frontal Chest Radiograph radiographic lung injury score (# of quadrants)
- 9. Vasopressors or inotropes (epinephrine, norepinephrine, phenylephrine, vasopressin, dopamine > 5  $\mu$ g/kg/min, dobutamine, phosphodiesterase inhibitors)
- 10. Suspected or known site of infection
- 11. Plasma CRP level
- 12. Blood for DNA banking (Appendix H)
- 13. Blood for cytokines, mediators, and markers of inflammation. Plasma obtained from two, 10 ml EDTA anti-coagulated blood samples will be divided immediately after centrifugation into 4 equal 2 ml aliquots in specified tubes and frozen at  $-70^{\circ}$ C.
- 14. Urine for cytokines, mediators and markers of inflammation. Urine obtained from the patients will be collected in an 8 ml sample tube and divided into 4 equal aliquots in specified tubes and frozen at  $-70^{\circ}$ C.

# 6.3. Assessments after Enrollment

The following data will provide the basis for assessing protocol compliance and safety as well as between-group differences in several efficacy variables. Data for each of the variables will be recorded on the days shown in the Time-Events schedule (Appendix F) or until death, discharge from the intensive care unit, or unassisted ventilation for 48 hours.

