#### Secondary Efficacy Variables:

- 1. Ventilator Free Days to day 28
- 2. Hospital mortality to day 28
- 3. Organ failure free days at day 14
- 4. ICU-free days at day 28
- 5. Hospital-free days at day 60

- 6. Increase in PaO2/FiO2 ratio and reduction in Oxygenation Index on study days 1-7 (to use ABGs as available)
- 7. Venous thromboembolism (VTE) to day 14
  - a. Documented by venous ultrasound, impedance plethysmography, contrast venography, ventilation-perfusion lung scan, CTPA/V, or pulmonary angiography
- 8. Composite end-point of myocardial infarction, bowel ischemia or ischemic stroke to study day 28
- 9. Arrhythmias during ICU stay or until day 14, whichever is first
- 10. Development of acute kidney injury (AKI)
- 11. Changes in plasma concentrations of CRP from day 0 to day 6 and day 14. Blood and urine will be reserved beyond study completion for additional biomarker studies.

**Focused Safety Analysis:** Incidence of elevations in CK > 10 times ULN or ALT > 8 times ULN as measured on days 0,1,3,6,14,21 (Appendix B)

**Study Drug Dosing:** All study drug doses will be administered via the enteric or oral route. Study drug will be blinded using an identical appearing placebo.

- 1. The first study drug dose (rosuvastatin or placebo) will be administered within 4 hours of randomization as a loading dose of 40 mg.
- 2. Subsequent doses will be at 10 am daily (+/- 4 hours) starting on the next calendar day as a maintenance dose of 20 mg.
  - a. If for any reason a maintenance dose is not administered at the intended time, it may be administered subsequently but not more than 12 hours after the intended time of administration.

Should the time be > 12 hours since last scheduled dose, the patient will not receive a dose on that study day but will be given a loading dose on the next calendar day. Maintenance dosing will continue on subsequent days.

Daily doses will be reduced by 50% for patients with a creatinine level of greater than or equal to 2.8 mg/dL who are not on renal replacement therapy. Loading doses will not be reduced.

Daily Dosing:

- Each subject will receive full dose if last known creatinine value is less than 2.8 mg/dL.
- Each subject will receive half dose if last known creatinine value is greater than or equal to 2.8 mg/dL (unless receiving renal replacement therapy in which case a full dose is given).

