#### **Reference Measurements**

The following parameters will be measured and recorded using values closest in time to 8:00 A.M. on the days specified in the Time-Events schedule (Appendix F). The following conditions will be ensured prior to measurements: no endobronchial suctioning for 10 minutes; no invasive procedures or ventilator changes for 30 minutes. All vascular pressures will be zero-referenced to the mid-axillary line with the patient supine.

- 1) If receiving assisted ventilation record daily up to day 7:
  - a) Tidal volume, FiO2, PEEP, inspiratory plateau pressure, and mean airway pressures
  - b) Pressure during inspiration if on a pressure targeted mode (PSV, PCV, etc).
  - c) Arterial PaO2, PaCO2, pH and SpO2
- 2) CK, AST, ALT as in schedule of events (Appendix F)
- 3) Fluid intake and output
- 4) Vital signs: Heart rate, systolic and diastolic blood pressure, body temperature, CVP
- 5) Modified Brussels Score data days 0-14:
  - a) Vasopressor use (Y/N), worst systolic BP, creatinine, bilirubin, and platelet count for the day. The date and value of the highest creatinine between days 15-28
- 6) CAM-ICU delirium screening assessment and RASS or RIKER sedation score through ICU discharge or study day 28 at select hospitals
- 7) Presence of myopathy
  - 8) Frontal Chest Radiograph Lung Injury Score
- 9) Occurrences of VTE, myocardial infarction, bowel ischemia, ischemic stroke and arrhythmias requiring treatment
- 10) Methylprednisolone equivalents greater than 20 mg
- 11) Daptomycin administration
- 12) Concomitant medications: niacin, fenofibrate, cyclosporine, gemfibrozil, lopinavir, ritonavir, or oral contraceptives. (Yes/No each day). The type and dose of statins prescribed as part of usual care if the study drug is withdrawn by the treating physician during the treatment period or prescribed after the treatment period will be recorded.
- a) Study drug/placebo will be stopped should one of these medications be started.
   13) Blood and urine for cytokines, mediators, and markers of inflammation. Plasma obtained from two, 10 ml EDTA anti-coagulated blood samples will be divided immediately after centrifugation into 4 equal 2 ml aliquots and frozen at -70°C. Urine obtained from the patients will be collected in an 8 ml sample tube and divided into 4 equal aliquots in specified tubes and frozen at -70°C. Specimens will be collected on days 3 and 6.
- 14) Plasma CRP levels on days 6 and 14

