# **APPENDIX F:** Time-Events Schedule

Measurement/Event	Day 0	1	2	3	4	5	6	7	8	9	10	12	14	21	28	60/ 90
Demographics, History & Physical, Height, Weight	Х															
AUDIT and smoking survey	Х															
Etiology of ARDS, site of sepsis	Х															
APACHE III Score	Х															
Brussels Score^	Х	X	х	х	Х	Х	Х	X	х	Х	Х	Х	Х			
GCS	Х							X					Х			
Ventilator Parameters (including FiO 2 ) *	Х	X	х	х	х			X				Х		X	х	
Arterial Blood Gases (PaO 2 , PaCO 2 , pH) and SpO 2	Х	A	A	А	A	А	А	Α					А	А	A	
Vital signs *	X	X	Х	Х	X	Х	X	X								
Blood Statin peak/trough level $^{\beta}$							Х									
Concomitant medications (Y/N)	Х	X	х	х	Х	Х	Х	X	Х	Х	Х					
Presence of myopathy €																
I/Os	Х	X	х	х	Х	Х	Х	X								
Occurrences of MI, VTE, ischemic stroke, bowel ischemia €																
Episodes of arrhythmias $^{\Omega}$	Х	X	Х	Х	Х	Х	Х	X	Х	Х	Х	Х	Х			
ALT β	Х	X	А	Х	А	А	Х	А	А	А	А	А	Х	X		
СК, β	Х	X	А	Х	А	А	Х	Α	А	Α	Х	А	Х	X		
AST	Х	х	А	х	А	А	х	А	А	Α	А	А	Х	Х		
Chest X-ray (LIS)	х	A	А	А	А	А	А	А	А	А	А					
Plasma CRP levels $^{\beta}$	Х						Х						Х			
Blood for DNA	Х															
Blood and Urine for markers of inflammation $^{\beta}$	Х			Х			х									
Study Drug Administration Record	Х	X	х	Х	х	Х	х	X	Х	Х	Х	Х	Х	X	х	
Vital Status															X	Х

X = Required

A=When available

\*Data gathered at times indicated or until patient achieves 48 hrs of unassisted breathing, whichever is sooner

€ Data gathered until 72 hours after study drug is discontinued

^Daily for 14 days or until ICU discharge and the date and value of the highest creatinine between day 15 and 28

 $^{\Omega}$  Data gathered until day 14 or ICU discharge, whichever occurs first

β These may be obtained plus or minus two days except for baseline and day 1. Attempt to maintain spacing between labs and samples if obtaining on days other than those specified.

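### Section 6.3 and Appendix F disagree on whether day-6 and day-14 CRP, a secondary endpoint, is drawn in patients who have left the ICU or are breathing unassisted

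*Protocol*

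**What the plan says.** The study summary lists as a secondary efficacy variable "Changes in plasma concentrations of CRP from day 0 to day 6 and day 14". Protocol section 3.3, item 10, repeats it: "Changes in plasma concentrations of CRP from day 0 to day 6 and 14". Section 3 adds: "Analysis of the primary, secondary and other endpoints will be conducted on an intention-totreat (as randomized) basis".

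Two places govern who is sampled.

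- **Section 6.3.** The opening paragraph covers every variable listed below it. Data are recorded on the days shown in Appendix F "or until death, discharge from the intensive care unit, or unassisted ventilation for 48 hours". Item 14 of that list is "Plasma CRP levels on days 6 and 14", with no exemption.
- **Appendix F.** The CRP row is marked as required on days 0, 6 and 14. Its only footnote is a timing window: "These may be obtained plus or minus two days except for baseline and day 1". Stops tied to recovery are attached to other rows. The rule "Data gathered at times indicated or until patient achieves 48 hrs of unassisted breathing, whichever is sooner" is on ventilator parameters and vital signs. The rule "Data gathered until day 14 or ICU discharge, whichever occurs first" is on arrhythmias, and the Brussels score has a similar ICU-discharge stop.

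**The concern.** The text and the table give a site different instructions for the same patient. Take someone who leaves the ICU on day 8 and is on a ward of the study hospital on day 14. Appendix F requires the CRP sample; section 6.3, read literally, has already stopped recording. That patient may also have received study drug until three days after ICU discharge (section 5.3).

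The protocol treats CRP as a possible marker of drug effect (section 6.3, item 14a) and expects statins to lower it (section 3.3). Under the literal 6.3 rule, whether CRP is measured depends on liberation from the ventilator and on ICU discharge. These are outcomes the drug is meant to improve: ventilator-free and ICU-free days are themselves secondary endpoints. The arms would then be compared among patients selected after randomization. An analysis plan cannot recover samples that were never drawn, so the sampling rule has to be settled in the protocol.

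**Working it through.** **1. The two rules side by side**

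| Patient's status on the CRP day | Section 6.3, literal | Appendix F |
|---|---|---|
| In ICU, not yet 48 h unassisted | draw | draw |
| In ICU, 48 h unassisted | stopped | draw |
| Left ICU, still in study hospital | stopped | draw |

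**2. Does section 6.3 settle the conflict itself?** It does not. It takes its days from Appendix F and then adds its own stop. Yet several items under the same sentence run past that stop: the highest creatinine on days 15 to 28 (item 5), statins prescribed after the treatment period (item 12), and, in Appendix F, myopathy and vascular events until 72 hours after study drug ends. The clause cannot apply to everything it covers, and nothing says which items are exempt.

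**3. Effect of the window.** With ±2 days, the day-6 sample may be drawn from day 4 and the day-14 sample from day 12. A patient who reaches 48 hours unassisted on day 5 can still have a day-6 sample under the literal rule. The loss therefore falls mainly on day 14, with some on day 6.

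**4. Precision (illustration).** The protocol gives no sample size, SD or expected completeness for CRP, so there is no stated figure to reproduce. The maximum sample size is 1000 (section 7.2), taken as 500 per arm. The share still sampled is assumed. For n per arm, the difference detectable with 80% power at two-sided 0.05 is (1.960 + 0.842) × √(2/n) SD.

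- All sampled, n = 500: 2.802 × 0.0632 = 0.18 SD
- 70%, n = 350: 2.802 × 0.0756 = 0.21 SD
- 50%, n = 250: 2.802 × 0.0894 = 0.25 SD
- 30%, n = 150: 2.802 × 0.1155 = 0.32 SD

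**5. Bias (illustration).** Assume a standard normal severity; a patient is sampled if severity exceeds c; CRP change has correlation ρ with severity; the drug lowers the severity that governs sampling by s SD but has no effect on CRP. Then bias = ρ × [λ(c + s) − λ(c)], where λ(x) = φ(x)/(1 − Φ(x)).

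- Low end (70% sampled, c = −0.524, s = 0.2, ρ = 0.3): 0.3 × (0.603 − 0.497) = 0.03 SD
- High end (30% sampled, c = 0.524, s = 0.3, ρ = 0.5): 0.5 × (1.386 − 1.159) = 0.11 SD

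Simulation over the grid gave the following, with CRP higher in the treated patients who are still sampled:

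| Control / treated sampled | s | Bias, ρ = 0.3 | Bias, ρ = 0.5 |
|---|---|---|---|
| 70% / 63% | 0.2 | 0.034 | 0.054 |
| 70% / 59% | 0.3 | 0.048 | 0.082 |
| 50% / 42% | 0.2 | 0.041 | 0.067 |
| 50% / 38% | 0.3 | 0.060 | 0.099 |
| 30% / 23% | 0.2 | 0.043 | 0.073 |
| 30% / 20% | 0.3 | 0.068 | 0.112 |

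With s = 0 the simulated bias lay between −0.004 and 0.002 SD, which is simulation noise around zero.

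**The case against.** The strongest reply is that Appendix F is the operative schedule. Section 6.3 cites it, the table assigns stops row by row, and the 6.3 sentence does not say that the earlier of its two limits governs, as the ventilator footnote does. Since a uniform stop would contradict other items in the same list, 6.3 is best read as a loose catch-all. This is the more coherent reading, and it defeats one inference a reader might draw: that day-14 CRP will definitely be measured only in unrecovered patients. The documents do not settle that. The reply does not remove the conflict, because neither place says which prevails and a site can follow either.

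A reader might also infer that a fixed share of any CRP effect would be lost. If CRP were itself the severity that decides sampling, a small effect would be multiplied by 1 + cλ − λ², with λ taken at c. That is 0.58, 0.49, 0.36, 0.31 and 0.26 for 80%, 70%, 50%, 40% and 30% sampled. The protocol does not support that premise. It describes an effect on CRP production (section 1.5), a CRP reduction in healthy volunteers given endotoxin (section 1.6), and a fall within 48 hours of starting a statin (Appendix C). An effect independent of severity is not attenuated by this selection.

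Nor do the documents show that rosuvastatin would be made to look worse. The multiplier above is always positive, so it shrinks a difference without reversing it. The wrong-direction result in the bias table needs a drug that speeds recovery and leaves CRP unchanged.

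Two further points stand. Analysis as randomized fixes the arms compared and does not promise complete samples. CRP is also the last-listed secondary endpoint and enters no power statement or stopping rule.

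**Conclusion.** The contradiction is real: section 6.3, read literally, and Appendix F differ on whether CRP is drawn after ICU discharge or 48 hours of unassisted breathing. If sites follow 6.3, CRP is missing in recovered patients, mainly on day 14. The comparison is then selected on a post-randomization outcome and loses precision.

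The size of the bias cannot be computed from the documents. It is about zero if treatment does not affect recovery, and otherwise depends on how closely CRP tracks the severity that decides sampling. The 0.03 to 0.11 SD range and the detectable differences of 0.21 to 0.32 SD rest on assumed sampled shares of 30% to 70%; the bias range also rests on assumed correlations of 0.3 to 0.5 and recovery shifts of 0.2 to 0.3 SD. The 0.18 SD reference assumes that every patient is sampled, which deaths and hospital discharges would prevent even under Appendix F. Severity is minor to moderate: a secondary biomarker endpoint is affected, and the primary analysis is not.

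**What to change.** Add one sentence to section 6.3: the stopping clause does not apply to item 14, and CRP is drawn on days 6 and 14, within the existing ±2-day window, in every patient alive and still in the study hospital, regardless of ICU discharge or unassisted breathing. This agrees with the CRP row of Appendix F. Report the number sampled by arm at each day.

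The cost is the sentence itself and at most two ward blood draws per patient. The change reduces the selection without removing it: patients who die or leave hospital before the draw will still have no value. How to handle those missing values can be left to the analysis plan.
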